TRIAL PROTOCOL

EMO

Eczema Monitoring Online

Eczema Monitoring Online via Questionnaires

Version 1.0 08-04-2021

Trial Co-ordinating Centre: Centre of Evidence Based Dermatology, University of Nottingham

Trial	Eczema Monitoring Online (EMO)	Protocol		Date:	08-04-2021	Page:	1 of 25
name:	Trial Protocol	version:	1.0				

Study Personnel and Contact Details:

Chief Investigator: [name]

Professor of Applied Dermatology Research Centre of Evidence Based Dermatology

University of Nottingham [name]

[name]

[contact]

Email: [contact]

Co-investigators: [name]

PhD student in Clinical Trials Research Centre of Evidence Based Dermatology

University of Nottingham [name]

[name]

Email: [contact]

[name]

Assistant Professor of Clinical Trials

Nottingham Clinical Trials Unit

University of Nottingham

[name]

[contact]

Email: [contact]

Trial Statistician: [name]

Assistant Professor of Medical Statistics and Clinical Trials

Nottingham Clinical Trials Unit

University of Nottingham

[name]

[contact]

Email: [contact]

Trial	Eczema Monitoring Online (EMO)	Protocol		Date:	08-04-2021	Page:	2 of 25
name:	Trial Protocol	version:	1.0				

Synopsis

Title	Eczema monitoring online via questionnaires
Acronym	EMO
Short title	Eczema Monitoring Online (EMO)
Chief Investigator	[name]
Aims and Objectives	AIM: The overall aim of this study is to inform the design of eczema randomised controlled trials on whether regular monitoring of eczema symptoms affects patient-reported outcomes.
	OBJECTIVES:
	To evaluate the effect of regular symptom monitoring on eczema severity
	To evaluate the effect of regular symptom monitoring on adherence to eczema treatment use
	To evaluate the effect of regular symptom monitoring on missing data
Trial Configuration	Online, two-arm, parallel group, randomised controlled trial.
Setting	The trial will be conducted online. Participants will be recruited via a variety of recruitment methods (including, but not limited to): social media, eczema charities, study participant recruiting websites and existing mailing lists of people who have taken part in previous eczema studies and consented to be contacted about future studies.
Sample size estimate	Assuming a standard deviation of 6.5, the estimated sample size to detect a between group difference of 2.5 in eczema severity score with 80% power and with a two-sided significance level is a total of 212 participants (106 per group). Allowing for 20% loss to follow up, the required total sample size for this trial is 266 participants (133 per group).
Number of participants	266 participants

Ī	Trial	Eczema Monitoring Online (EMO)	Protocol		Date:	08-04-2021	Page:	3 of 25
	name:	Trial Protocol	version:	1.0				

Eligibility criteria	
_ iigioiity ontona	Inclusion Criteria:
	 Self-report or parent/carer report of eczema diagnosis by a healthcare professional Person aged 1 year or older Able and willing to provide informed consent If under 16 years old, a parent/carer needs to provide informed consent on behalf of the child Able to read and understand written English Have access to the internet and to an internetenabled device POEM score of 3 or above at eligibility screening Exclusion Criteria: Unable/unwilling to provide informed consent Currently taking part in another eczema clinical trial
	omnour than
Description of the intervention	The intervention will be the online Patient Oriented Eczema Measure (POEM) questionnaire. Participants in the intervention group (Weekly group) will be asked to complete POEM weekly. The control group will not receive intervention.
Duration of study	The overall duration of the study is anticipated to be approximately 21 months and planned to start in June 2021. Each participant will be asked to participate in the trial for 8 weeks.
Randomisation and	The randomisation schedule is based on computer generated
blinding	random codes, using random permuted blocks of randomly
	varying size, stratified by age and baseline disease severity.
	The PhD student will deal with participant queries, thus she
	will have access to group allocation, but the other trial team
	members and the trial statistician will remain blinded.
Outcome measures	The primary outcome will be eczema severity measured by the self-reported or proxy (parent/carer reported) POEM at baseline and 8 weeks.
Methods of analysis	The primary outcome will be analysed according to randomised groups. The primary analysis of POEM scores will be performed using single linear regression and will adjust for stratification variables (age and baseline disease severity) and for other variables that appear to be imbalanced at baseline. Sensitivity analyses and other further exploratory analyses will be performed using appropriate statistical methods.

Т	rial	Eczema Monitoring Online (EMO)	Protocol		Date:	08-04-2021	Page:	4 of 25
n	ame:	Trial Protocol	version:	1.0				

Abbreviations:

CEBD Centre of Evidence Based Dermatology

CONSORT CONsolidated Standards of Reporting Trials

CRF Case Report Form

CI Chief Investigator

CLOTHES Clothes for the Relief of Eczema Trial

ECO Eczema Care Online

GCP Good Clinical Practice

GDPR General Data Protection Regulations

HOME Harmonising Outcome Measures for Eczema

MCID Minimal Clinically Important Difference

PIS Participant Information Sheet

POEM Patient-Oriented Eczema Measure

REC Research Ethics Committee

REDCap Research Electronic Data Capture

RCT Randomised Controlled Trial

SR Systematic Review

SWET Softened Water for Eczema Trial

UoN University of Nottingham

Trial	Eczema Monitoring Online (EMO)	Protocol		Date:	08-04-2021	Page:	5 of 25
name:	Trial Protocol	version:	1.0				

TABLE OF CONTENTS

Study Personnel and Contact Details	2
Synopsis	3
Abbreviations	5
1. Background and Rationale	8
1.1 Background	8
1.2 Trial Rationale	8
1.2.1 Justification for Participant Population	9
1.2.2 Justification for Design	9
1.2.3 Choice of Treatment	9
2. Aims, Objectives and Outcome Measures	9
2.1 Aims	9
2.2 Objectives	9
2.3 Outcome Measures	9
3. Trial Setting	10
3.1 Trial Setting	10
4. Eligibility	11
4.1 Inclusion Criteria	11
4.2 Exclusion Criteria	11
5. Consent	12
6. Enrolment and Randomisation	12
6.1 Enrolment	12
6.2 Randomisation	13
6.3 Blinding	13
7. Trial Intervention	14
7.1 Intervention	14
8. Trial Procedures and Assessments	14
8.1 Summary of Assessment	14
8.2 Schedule of Assessments	15
8.3 Trial Assessments	16
8.4 Withdrawal Procedures	17
9. Adverse Event Reporting	17
10. Data Handling	17
10.1 Case Report Form	17
10.2 Source Data	17
10.3 Data Management	17

Trial		Eczema Monitoring Online (EMO)	Protocol		Date:	08-04-2021	Page:	6 of 25
nam	e:	Trial Protocol	version:	1.0				

11. Quality Control and Quality Assurance	18
11.1 Study Conduct	18
11.2 Study Data	18
11.3 Record Retention and Archiving	18

1.1 Background

Eczema (also known as atopic eczema, atopic dermatitis) is a common, chronic, inflammatory skin condition that causes itchiness, sleep loss and decreased quality of life, affecting children and adults (1). It is characterised by periods of relative remission and relapse with increased disease activity, indicating the fluctuating nature of the disease (2). This should be taken into account when designing clinical trials that evaluate the effectiveness of eczema interventions. In the last two decades a lot of randomised controlled trials (RCTs) in eczema have been conducted (3). Online questionnaires completed by participants are often used in eczema clinical trials to capture the views of participants about their eczema. This allows researchers to measure the effectiveness of different treatments (4). Findings of the CLOTHES and SWET eczema RCTs show that completing questionnaires regularly (known as monitoring) can change the way that people manage their eczema, indicating a behaviour change, resulting in improved eczema severity (5,6). This is a concern within clinical trials because completing regular questionnaires may make it harder to identify changes in the eczema resulting from the treatments being tested. The effect of monitoring on trial outcomes is well described in other chronic conditions, such as cancer, asthma and HIV (7,8,9). One proposed mechanism of action of monitoring is associated with participants' behaviour change, as illustrated in recent systematic reviews (10,11). This online trial has been designed to test our primary hypothesised mechanism of action of participant behaviour change.

The Harmonising Outcome Measures for Eczema (HOME) initiative recognises the importance of monitoring and also the frequency of outcome measure collection (12,13). HOME is a global collaboration of patients, healthcare professionals, journal editors, regulatory authorities and the pharmaceutical industry, working collaboratively to standardise outcome measures in eczema clinical trials (14). In RCTs, a balance needs to be established between capturing accurate measurements of the outcome of interest, whilst not unduly altering the behaviour and attitudes of the trial participants.

Further research is needed to evaluate the effect of monitoring on outcomes. To date, to the best of our knowledge, no study has been conducted to capture the effect of monitoring in eczema. This methodological trial is specifically designed to investigate whether completing questionnaires is an effective intervention in improving eczema severity. This will allow us to evaluate the effect of regular monitoring on eczema severity and help to improve the design of future eczema clinical trials.

1.2 Trial Rationale

This study aims to assess whether completing questionnaires regularly changes participants' behaviour and affects adherence to standard treatment use and management of eczema. It is important to investigate the effect of monitoring on clinical outcomes as it can cause erroneous estimation of the treatment effect. The term 'monitoring' will be used to denote completion of self-reported or proxy (parent/carer) reported questionnaires. This online trial will help to evaluate whether monitoring affects disease severity and will inform future eczema clinical trial designs about the effect of monitoring on patient-reported outcomes.

Trial	Eczema Monitoring Online (EMO)	Protocol		Date:	08-04-2021	Page:	8 of 25
name:	Trial Protocol	version:	1.0				

1.2.1 Justification for Participant Population

Eczema is a common chronic skin condition, affecting both children and adults with varying disease severity (1). Adults and children with eczema with any disease severity (mild, moderate and severe) will be eligible to participate in this trial. The broad aim of this study is to inform the design of future eczema clinical trials therefore the eligibility criteria is diverse, which improves the generalisibility of the study.

1.2.2 Justification for Design

This is an online, two-arm, parallel group RCT. Participants with eczema will be randomised (1:1) to complete online questionnaires weekly (Intervention group) or at the beginning and end of study only (Control group). Online questionnaires are often used in eczema trials therefore we are replicating what is usually done in those trials; namely, asking participants to complete questionnaires online. This is not a treatment trial, therefore there is no need for face-to-face visits to take place. Moreover, it is feasible to conduct this remote study, especially under the current COVID-19 pandemic. The online design also allows this methodological study to be conducted efficiently.

1.2.3 Choice of Treatment

The intervention in this trial is questionnaire completion and therefore there is no treatment involved. Participants will be asked to complete questionnaires at different timepoints according to their randomised allocation. Participants will be able to continue to use their existing eczema treatments as usual.

2. Aims, Objectives and Outcome Measures

2.1 Aims:

The overall aim of this study is to inform the design of future eczema randomised controlled trials on whether regular symptom monitoring affects patient-reported outcomes.

2.2 Objectives:

- 1. To evaluate the effect of regular symptom monitoring on eczema severity
- 2. To evaluate the effect of regular symptom monitoring on adherence to eczema treatment use
- 3. To evaluate the effect of regular symptom monitoring on missing data

2.3 Outcome Measures:

Primary outcome:

 Eczema severity: change in eczema severity from baseline to 8 weeks assessed by the Patient Oriented Eczema Measure (POEM) score. POEM is a HOME

Trial	Eczema Monitoring Online (EMO)	Protocol		Date:	08-04-2021	Page:	9 of 25
name:	Trial Protocol	version:	1.0				

recommended core outcome set instrument for the patient-reported symptoms domain (15). It captures self-reported or proxy reported symptoms, including: frequency of itch, sleep disturbance, bleeding, weeping/oozing, cracking, flaking and dryness. It provides a score from 0 to 28, with higher score meaning more severe eczema (16).

Secondary outcomes:

- Adherence to eczema treatment use: will be assessed in two ways:
 - Change in eczema treatment use from baseline to 8 weeks assessed by emollient and topical corticosteroid use over the last week.
 - Change in eczema treatment use from baseline to 8 weeks assessed by overall eczema treatment use over the last 2 months.
- Missing data: the proportion of fully completed questionnaires at 8 weeks.

[figure not shown]
3. Trial Setting

3.1 Trial Setting

This study will be conducted online. Participants will be recruited via various methods, including but not limited to: social media (e.g. Facebook, Twitter, Instagram), eczema charities (e.g. National Eczema Society), participant recruitment websites (e.g. www.callforparticipants.com) and existing mailing lists of people who have taken part in previous eczema studies and consented to be contacted about future studies. We aim to recruit both children and adults with eczema.

Trial	Eczema Monitoring Online (EMO)	Protocol		Date:	08-04-2021	Page:	10 of 25
name:	Trial Protocol	version:	1.0				

Figure 1. Participant flow through this trial:

4. Eligibility

4.1 Inclusion Criteria

- Self-report or parent/carer report of eczema diagnosis by a healthcare professional
- Person aged 1 year or older
- Able and willing to provide informed consent
- If under 16 years old, a parent/carer needs to provide informed consent to participate
- Able to read and understand written English
- Have access to the internet and to an internet-enabled device
- POEM score of 3 or above at eligibility screening

4.2 Exclusion Criteria:

- Unable/unwilling to provide informed consent
- Currently taking part in another eczema clinical trial

Trial	Eczema Monitoring Online (EMO)	Protocol		Date:	08-04-2021	Page:	11 of 25
name:	Trial Protocol	version:	1.0				

5. Consent

Adults and children with eczema will be recruited via various methods (including, but not limited to) social media, eczema charities, participant recruitment websites, existing mailing lists of people who have taken part in previous eczema studies and consented to be contacted about future studies. A link to the study website will be displayed in the advertisement/email/information/website about the study. People interested in the study will follow the link, which directs them to the study website. The Participant Information Sheet (PIS) will be displayed, which will contain the summary of the aim of the research, intervention, eligibility criteria and what will happen to their data upon withdrawal from the study. The PIS will stress that participation is voluntary and the potential participant may withdraw from the trial at any time without any negative consequences. It will also explain that participants can withdraw from the study by notifying us via sending an email to the study email address. There will be a statement that makes it clear that by clicking the NEXT button, that allows them to proceed to the consent form, they are agreeing to the information provided.

Upon clicking the NEXT button, the online consent form will be displayed, and potential participants will be required to read and complete the form and they will be asked to type their name. According to the UK Health Research Authority (17) this is an appropriate electronic method to seek and document consent for this type of study. If a child is below 16 years of age and wishes to participate in the study, the parent/carer will be asked to provide informed consent on behalf of the child. Potential participants will be informed that by proceeding to submit the online consent form, they are agreeing that they have read and understood the information provided, fulfil the eligibility criteria and are willing to voluntarily take part in this study. A completed online consent form from each participant will be always obtained prior to participating in this trial. Electronic data, including consent forms, will be managed, stored and organised according to the study Data Management Plan.

6. Enrolment and Randomisation

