6.1 Enrolment

Potential participants will be recruited via different organisations and platforms (including, but not limited to):

- Eczema charities: e.g. National Eczema Society (http://www.eczema.org/),
 Eczema Outreach Support (https://www.eos.org.uk/), Nottingham Support Group for Carers of Children with Eczema (http://www.nottinghameczema.org.uk/index.aspx).
- School of Medicine / Centre of Evidence Based Dermatology communication channels (e.g. Twitter, website, existing mailing lists and newsletters).

Trial	Eczema Monitoring Online (EMO)	Protocol		Date:	08-04-2021	Page:	12 of 25
name:	Trial Protocol	version:	1.0				

- Call for Participants website (https://www.callforparticipants.com). An open platform that brings together researchers to promote their studies and potential participants interested in taking part in studies.
- **Social media:** the study will be advertised on a range of platforms e.g. Facebook, Twitter, Instagram.
- Other organisations/online platforms/ individuals e.g. resharing via social media.

Recruitment is expected to start in June 2021 and it is anticipated to last for approximately 9 months. Participant retention and completion of follow-up assessments will be promoted by using various methods (including, but not limited to): email reminders, text reminders, telephone calls. Newsletters and other appropriate communications may be used to aid retention. Upon completion of the follow up questionnaires at 8 weeks, participants will be able to enter an optional price draw for a chance to win one of six £20 vouchers to say thank you for taking part. The recruitment strategy will focus on the UK, as participation is online so it will not be restricted by geography.

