6.2 Randomisation

Participants will complete the consent form followed by baseline characteristics and eligibility screening. All assessments and questionnaires will be developed by using the Research Electronic Data Capture (REDCap) software. Those who do not fulfil the eligibility criteria of a POEM score of 3 or above will be provided with information explaining that they were not eligible to take part in the study and will be signposted to other online resources.

Eligible participants will be randomised online to either the intervention group or to the control group, using the REDCap software. The randomisation schedule will be based on computer generated random codes, using random permuted blocks of randomly varying size, stratified by age and baseline disease severity.

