6.3 Blinding

This is a methodological trial and there will be no treatment intervention involved.

The nature and the objectives of this study does not allow complete transparency towards participants about the purpose of this trial. If they knew the aim of the trial, it would likely influence their behaviour, which would completely undermine the trial objectives. Therefore, potential participants will be told that the aim is to evaluate how eczema changes over time. It appears to be an appropriate approach as this is a non-treatment intervention trial and participants will not be at disadvantage or risk because of taking part. After randomisation, participants will be informed about how often they will be asked to complete the questionnaires. The PhD student will deal with participant queries, thus she will have access to group allocation, but the other trial team members and the trial statistician will remain blinded.

Trial	Eczema Monitoring Online (EMO)	Protocol		Date:	08-04-2021	Page:	13 of 25
name:	Trial Protocol	version:	1.0				

7. Trial Intervention

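### No limit of one participant per household: one parent can be weekly monitor for one child and proxy for a control child, diluting the contrast

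*Protocol*

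**What the plan says.** Section 4.2 contains two exclusions: being unable or unwilling to consent, and "Currently taking part in another eczema clinical trial". The second concerns other trials, not a relative already enrolled in this one. The synopsis repeats the same list. Entry is wide: "Person aged 1 year or older" (section 4.1), with adults and children both sought (section 3.1).

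For a child under 16, "the parent/carer will be asked to provide informed consent on behalf of the child" (section 5). Parents may also supply the data, since section 1.2 states: "The term 'monitoring' will be used to denote completion of self-reported or proxy (parent/carer) reported questionnaires". Section 1.1 gives participant behaviour change as the primary hypothesised mechanism.

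Recruitment is online and open. Its channels (section 6.1) include charities, social media resharing and the "Nottingham Support Group for Carers of Children with Eczema". Allocation is by individual, "using random permuted blocks of randomly varying size, stratified by age and baseline disease severity" (section 6.2), with no household unit or stratum. Controls receive no questionnaires from week 1 to week 7 (section 8.2).

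On concealment, section 6.3 says: "If they knew the aim of the trial, it would likely influence their behaviour, which would completely undermine the trial objectives". The same section has participants told, after randomisation, how often they will be asked to complete questionnaires.

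**The concern.** In most eczema trials, two siblings in different arms receive different treatments and little passes between them. Here the exposure is the act of reporting. When a parent reports by proxy, the parent is the person monitored and may well also be the person who manages the child's eczema. If one child is allocated to weekly POEM and a sibling to control, that parent is prompted every week while the sibling is analysed as unmonitored. Any change in the parent's habits can reach both children, so the difference between arms shrinks.

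At stake is the meaning of a null result. The trial is meant to tell designers of future trials whether monitoring alters patient-reported outcomes, and dilution makes a finding of little or no effect harder to interpret. A secondary risk is that a parent holding two schedules sees the one feature that differs between arms. Both problems arise at enrolment, so an analysis plan cannot undo them afterwards.

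**Working it through.** **Inputs.** From section 13.1: SD 6.5, difference 2.5 POEM points, 80% power, two-sided test, 106 per arm evaluable, 20% loss, 266 randomised. The significance level is not printed; 5% is assumed. Allocation is 1:1 (section 1.2.2). Two quantities are not in the documents and are assumed: *f*, the share of controls whose household also has a weekly participant, and *c*, the share of the effect that carries over to them.

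**The plan's own figure.** Per arm, n = 2 × [6.5 × (1.960 + 0.842) / 2.5]² = 106.1, which matches 106 to the nearest whole number. Then 106 / 0.8 = 132.5, so 133 per arm and 266 in total. The stated size reproduces.

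**How *f* relates to families.** Let *s* be the share of all participants enrolled as one of a pair from a household. With individual 1:1 allocation, a control in a pair has about a one-half chance that the relative is in the weekly arm, so f ≈ s / 2.

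**Dilution.** Expected difference = 2.5 × (1 − f × c).

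**Power.** Two-sample t test, 210 degrees of freedom, non-centrality = (difference / 6.5) × √(106 / 2). Undiluted: (2.5 / 6.5) × 7.28 = 2.80, giving 79.6%. With full carry-over (c = 1):

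| Controls affected, *f* | Participants in pairs, *s* ≈ 2f | *s* × 266 | Difference | Power |
|---|---|---|---|---|
| 0 | 0 | 0 | 2.5 | 79.6% |
| 1% | 2% | about 5 | 2.475 | 78.8% |
| 2% | 4% | about 11 | 2.45 | 78.0% |
| 5% | 10% | about 27 | 2.375 | 75.4% |
| 10% | 20% | about 53 | 2.25 | 70.8% |

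A normal approximation gives nearly the same: 80.0% undiluted, then 78.4%, 75.8% and 71.2% at 2%, 5% and 10%.

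**Partial carry-over.** Only the product f × c matters. With c = 0.5, the 10% row becomes the 5% row (75.4%) and the 2% row becomes the 1% row (78.8%).

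**Baseline adjustment.** The primary analysis adjusts for baseline severity (section 13.3). If the correlation of baseline with week-8 POEM is 0.5 (assumed), the residual SD is 6.5 × √(1 − 0.25) = 5.63. Power is then 89.6% undiluted, 86.4% at f = 5% and 82.6% at f = 10%, with full carry-over.

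**Standard errors.** Relatives' scores are correlated, while a single linear regression treats them as independent. Same-arm pairs raise the variance of the difference and split pairs lower it; with about half of each, the two roughly cancel. A simulation with 212 participants, unit SD, within-pair correlation 0.5 and no effect gave a true standard error of 0.1372 against a model value of 0.1371 when 20% were in pairs, and 0.1369 against 0.1370 when all were. Type I error stayed between 4.9% and 5.1%.

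**The case against.** The strongest objection is that nobody knows whether this would happen often enough to matter. For 5% or 10% of controls to be affected, about 10% or 20% of participants must enrol with a relative. One carers' group among many open channels, in a trial that also recruits adults, does not establish that. Full carry-over is a second generous assumption, least convincing for an affected parent and child. This stands: the lower rows of the table are upper scenarios, and at 1% or 2% the loss is under two percentage points.

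A reader might infer that the trial is underpowered. The documents do not support that, because the frequency is unknown and adjustment for baseline may well offset the loss.

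A reader might also infer that the regression's standard errors are wrong because family members are correlated. That is a result for cluster-randomised designs; under individual 1:1 allocation it does not follow, as shown above.

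A third tempting reading is that seeing both schedules reveals the purpose. Section 6.3 conceals the aim, not the schedule, and two different frequencies are compatible with the stated aim of seeing how eczema changes over time. Members of one support group could also compare schedules, which a household rule would not prevent. A hint is plausible; disclosure is not established.

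Finally, a household check could sit in the REDCap screening form or the Data Management Plan, which the protocol does not reproduce, or in Figure 1, which could not be consulted. That is possible, but the eligibility lists are complete in the text and are where such a rule belongs.

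**Conclusion.** The point holds as a gap in eligibility. Section 4 allows several participants per household and per reporting parent in a trial whose intervention is reporting itself. The expected consequence is dilution towards zero, provided that monitoring has an effect and that some of it reaches the control relative. The size is unknown and can be given only as a range: from 79.6% power to between 78.8% and 70.8% for 1% to 10% of controls affected. This assumes two-sided alpha 5%, SD 6.5, 106 per arm and full carry-over. A hint at the concealed purpose is a secondary and less certain risk. The argument does not rest on the standard errors. It is a cheap improvement to make before recruitment, not a flaw that invalidates the design.

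**What to change.** Add to section 4.2 and to the synopsis: *Another member of the same household is already enrolled in this trial.* Check it mainly by one screening question in REDCap. Postcode (collected for the UK only, section 8.2) and contact details can prompt a query but should not decide eligibility: participation is not restricted by geography, and a matching postcode does not prove a shared household. Because the wording refers to someone already enrolled, a family whose first member scores below 3 on POEM can still put forward another.

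The cost is one criterion, one screening item and a small loss of recruits. The 212 and 266 are unchanged, since that calculation already assumes independent, uncontaminated participants. If the rule is added after ethics approval, it would go through the amendment route in section 15.

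If the sponsor would rather not turn families away, the alternative is to randomise by household and allow for clustering in the analysis. That also removes split households, but the sample size would have to be reconsidered.
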